| | 
6.1 Thoroughly describe the study design.
 
This study consists of two phases. Phase 1 will be a randomized controlled trial (RCT). Having a controlled group is the gold standard to measure the efficacy of an intervention (Polit & Beck, 2021). RCTs provide the most persuasive evidence on whether one variable has a causal influence on another. RCTs' main strength is the certainty with which causal links may be determined. Kolb's learning theory serves as the underpinning for this study (Kolb & Kolb, 2009; Kolb, 1984).
 
Manipulation: The researcher will do a cold debriefing (after one-day post-simulation) for undergraduate nursing students in the intervention group.
 
Control: The control group will do a hot debriefing (immediately after the simulation).
 
Randomization: The researcher will assign the participants to a control or experimental based on number generator.
 
Once participants complete Phase 1, we will record their progress on REDCap. If they chose to only participate in Phase 1, we will mark their status as "completed" on REDCap. If they expressed interest in Phase 2, we will randomly select 16 participants from the pool based on a number generator and update their status on REDCap for Phase 2.
 
Outcome: The study outcome is BLS competence level. The competence level will be measured AHA (2020) BLS competency Checklist. First, the control and experiment groups will complete a pre-test on BLS competence. Both groups will do a pre-test. After finishing
 |

TEMPLATE: RESEARCH PROTOCOL

| NUMBER | ACTIVE DATE | PAGE |
|---------|-------------|----------|
| HRP-503 | 02-04-2020 | 10 of 40 |

the pre-test, we will do the randomization process. Then the intervention group will receive (cold debriefing); the control group will have the (hot debriefing). Both groups will do the post-test immediately after the debriefing session and another post-test after 24 hours of the first post-test.

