For phase 2, we will do a qualitative descriptive design with focus groups interview. Themes relating to hot and cold debriefing will be generated using a focused qualitative interview technique. Focused interviews are loosely structured interviews in which the interviewer guides the participant through a set of questions (Polit & Beck, 2021). Throughout the guide, participants are encouraged to share their own experiences and discuss all topics freely. Researchers can obtain all necessary information utilizing this technique, and participants will have the capability to provide illustrations and explanations (Polit & Beck, 2021).

6.2 Detail the procedures being performed, specifically the interaction or intervention with human subjects and/or their identifiable information. Please be clear and concise and provide information relevant to the current study. For example, please be sure that what will be done for this research is explained and differentiated from activities that have already taken place or will be submitted for future review. Please note that details about recruitment and consent are asked in later questions.

Potential participants will access the REDCap link to answer the eligibility questions (1) if they are above 18 years of age and (2) if they are senior or third year undergraduate nursing students. If they are eligible, they will enter their demographic on REDCap. After that, The PI will assign the participants to a hot or cold debriefing group based on a number generator. Participants will do a baseline BLS competence where they will do a simulation experience related to the competence of BLS, which is conducted as part of the study design. There will be a scenario about a nurse taking care of their client at a hospital, and when the nurse enters the client's room to check on their client, they find that their client is unresponsive. Nursing students are expected to start the process of Basic Life support. Nursing students are expected in the simulation to check the client's

TEMPLATE: RESEARCH PROTOCOL

| NUMBER | ACTIVE DATE | PAGE |
|---------|-------------|----------|
| HRP-503 | 02-04-2020 | 11 of 40 |

responsiveness, activate the cardiopulmonary arrest code, begin cardiopulmonary resuscitation, and give 30 compressions and 2 breaths. They will attach an automated external defibrillator and follow the instruction of the machine. The total scenario will last up to 5 minutes.

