Another interaction with participants will be the debriefing experiences, where students will do a group debriefing. Afterward, participants in the hot debrief group will do their post-test immediately after their debrief on the same day as the simulation, and another post-test after 24 hours of the first post-test. And then, the cold debrief participants will do the simulation, wait 24 hours, have the debrief, and will do an immediate post-test, and another post-test after 24 hours of the first post-test. The simulation will be conducted in order to complete the BLS assessment checklist at baseline, post-test, and second post-test. The same simulation and BLS Assessment checklist will be conducted at baseline, post-test, and second post-test. The BLS competence and DES will be administered online via REDCap. During the qualitative phase, participants will engage in a focus group which will be the final interaction. Random sampling will be used to select subsamples from both hot and cold groups for the focus group..

6.3 Describe procedures being performed to monitor subjects for safety or minimize risks.

The study carries minimal risk. Potential participants will not be expected to expose more than what they might face in a simulation experience that they are familiar with. Participants will be informed that they can choose to participate or not and can withdraw at any time. They can also decline to answer any questions that make them uncomfortable. The PI will receive training from the Co-PI/Faculty Advisor to monitor participants for any psychological stress during study phases. The PI and Co-PI/Faculty Advisor will meet weekly to discuss interactions with participants and ensure that the procedures for managing data protect confidentiality.

6.5 Where applicable, list and describe the data collection tools such as surveys, data collection forms, etc. All tools described should be uploaded in the RAP Smart Form on the Local Site Documents page unless they are standardized, validated tools.

For Phase 1

- (A) Demographic
- (B) BLS Competence Checklist

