The baseline BLS Competence level will be measured via the AHA (2020) BLS competency checklist. The BLS Competence assessment will be conducted by the primary investigator and/or [name] (Co-PI). All of the tests (Baseline, post-test, and second post-test) will be measured by the same tool of the AHA (2020) BLS competency checklist. The simulation will be conducted in order to complete the BLS assessment checklist at baseline, post-test, and second post-test. The same simulation and BLS Assessment checklist will be conducted at baseline, post-test, and second post-test.

- (C) Debriefing Tool
- (D) The Debriefing Experience Scale

TEMPLATE: RESEARCH PROTOCOL

NUMBER

ACTIVE DATE

PAGE

HRP-503

02-04-2020

12 of 40

| Phase 1 | | | | | | | |
|--------------------------|--|---------------------|----------|------------|---------------------|--------------------|--|
| Construct | Measure name | Minutes to complete | Baseline | Debriefing | Immediate Post test | 24-hours post-test | |
| (A) Demographics | Demographic (6 items) age, gender, Race, ethnicity, Finished credits hours, GPA, BLS certificate. | 5 minutes | X | | | | |
| (B) BLS Competence level | AHA (2020) BLS competency Checklist. there are 15 items, for each item 0 (not done or done incorrectly) and 1 (done correctly). | 5 minutes | X | | X | X | |
| (C) Debriefing Tool | The PEARLS Healthcare Debriefing Tool The tool has five domains (Bajaj et al., 2018) : (1) Setting the Scene, (2) Reactions, (3) Description, (4) Analysis, and (5) Application/Summary | 10 minutes | X | | | | |

TEMPLATE: RESEARCH PROTOCOL

| NUMBER | ACTIVE DATE | PAGE |
|---------|-------------|----------|
| HRP-503 | 02-04-2020 | 13 of 40 |

| | | | | | | | | | | |
|---------|--|--|--|------------|----|----|----|---|--|--|
| | | (D) Debriefing Experience Scale | The Debriefing Experience Scale (DES) (Reed, 2009, 2012) 20 items in total and was split into four subscales: (1) Analyzing Thoughts and Feelings; (2) Learning and Making Connections; (3) Facilitator Skill in Conducting the Debriefing; and (4) Appropriate Facilitator Guidance (Reed, 2009, 2012). The items on the scale were rated in two different areas: the "experience" for the student and the "importance" of the simulation experience (Reed, 2009). The 20 items were scored on a Likert scale of 1 (strongly disagree) to 5 (strongly agree) (Reed, 2009). | 10 minutes | X | | | | | |
| | | Total minutes | Total data collection minutes each visit | | 30 | 10 | 20 | 5 | | |

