| Phase 2 | | | | | | | | | | |
| | | 
The data collection will use a Semi-structured interview, the most common sort of interview used in this methodology, and it is the primary method of data collection (DeJonckheere & Vaughn, 2019). It will be included open-ended questions related to the participants' overall experience in terms of emotions, feelings, challenges, and learning. All the interviews will be conducted in a private place, and the PI will do all the interviews so the participants' interactions and questions will be consistent.
 
The general initial questions will be the same for the hot and cold debriefing group are:
 
(1) Tell me about your experience with simulation and what that's looked like for you?
 
(2) Tell me about your experience in debriefing?
 | | | | | | | | |

TEMPLATE: RESEARCH PROTOCOL

| NUMBER | ACTIVE DATE | PAGE |
|---------|-------------|----------|
| HRP-503 | 02-04-2020 | 14 of 40 |

(3) What did you like in debriefing?
 (4) How did debriefing help you to reflect on your simulation experiences?
 (5) Did you face any challenges during your experience?
 (6) What did you not like with debriefing?
 (7) How has debriefing impacted your ability to learn concepts or attain competency in your nursing skills.
 (8) How did debriefing impact your confidence in performing at the bedside?
 (9) Do you have any advice for educators who are designing simulation scenarios?
 (10) Is there anything else you would like to share?

6.6 Describe all data that will be accessed and collected during the study and how that data will be obtained (how it will be accessed).

All data that will be accessed and collected during the study is described in Section 6.5 above.

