| 9.0 STUDY TIMELINES | 
9.1 Describe the duration of an individual subject's participation in the study. List the number of study visits or frequency of study visits.
 
Phase 1:
 
The participants will be asked to fill in the demographic data (5 minutes). Baseline BLS Competence level (5 minutes). After that, PEARLS Healthcare Debriefing Tool will (10 minutes). After debriefing, students will complete a survey about their debriefing experience (10 minutes). Finally, a post-test BLS Competence level (5 minutes) and another post-test BLS Competence level after 24 hours for both groups (5 minutes).
 |

TEMPLATE: RESEARCH PROTOCOL

| NUMBER | ACTIVE DATE | PAGE |
|---------|-------------|----------|
| HRP-503 | 02-04-2020 | 16 of 40 |

| | |
|--|--|
| | 
Phase 2: 45-60 minutes of focus group interview.
 
9.2 Describe the timeline allotted for the enrollment of subjects. From 08/24/23 to 11/01/23
 
9.3 Describe the estimated date for the investigators to complete this study (complete primary analysis). We estimate that data analysis will be completed by May 1, 2024.
 |
| | 
10.1 Describe how subjects will be screened for eligibility.
 
The PI will ask permission from the student affairs office of the undergraduate nursing student to send an email to potential participants. Potential participants will be contacted via the UC email, and we will post flyers in the simulation lab at the CON. Potential participants will access the REDCap link or scan the QR code to answer the eligibility questions (1) if they are above 18 years of age and (2) if they are senior or third year undergraduate nursing students. The potential participant will also indicate in REDCap if they want to participate in phase 2 (focus group). In case there are over 16 participants who want to participate in phase 2, we will randomly choose 8 participants from the hot debriefing group and another 8 participants from the cold debriefing group. If they are eligible, they will enter their contact details, such as their name, email, and phone number(s) on REDCap. Alternatively, they may also contact the PI via email or phone. Once a potential participant's response is received, the PI will contact them to verify their eligibility and contact information.
 |
| | 
10.2 Describe/list the inclusion/exclusion criteria for the study. Senior or Third Year Undergraduate Nursing students who are above 18 years old.
 |

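### Debriefing is delivered in groups, but the t-tests for hypotheses 1b and 2 ignore the session and no session identifier is listed; if scores within a session are positively correlated, the type I error exceeds 5%

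*Protocol*

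**What the plan says.** Assignment is by individual (protocol 6.1): "The researcher will assign the participants to a control or experimental based on number generator". No text assigns whole groups. Delivery is to groups (protocol 6.2): "Another interaction with participants will be the debriefing experiences, where students will do a group debriefing". Hot debriefing follows the simulation at once and cold debriefing comes a day later (6.1), so by implication each session belongs to one arm.

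For hypotheses 1b and 2, protocol section 17.1 and the SAP both specify an independent t-test at p<0.05. Neither mentions a session term, a clustered variance or a design effect, and the sample size statement makes no allowance for clustering.

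Section 6.5 lists four items for phase 1: demographics, BLS checklist, debriefing tool and DES. Section 6.6 adds: "All data that will be accessed and collected during the study is described in Section 6.5 above". No session, group or facilitator identifier appears in the list.

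Four details bear on session size. On the scenario (6.2): "The total scenario will last up to 5 minutes". On scoring (6.5): "The BLS Competence assessment will be conducted by the primary investigator and/or" the co-investigator. Both arms repeat the simulation straight after debriefing as the first post-test (6.1, 6.2). The debriefing is allotted 10 minutes (6.5 table, 9.1).

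**The concern.** An independent t-test treats every student's score as a separate piece of information. Students debriefed together share a discussion, a facilitator and an occasion, so their later scores may resemble one another. Because each session sits within one arm, a shared session effect does not cancel in the comparison of arms. If the within-session correlation is positive, the standard errors are too small, the 95% confidence intervals are too narrow, and p<0.05 is weaker evidence than stated.

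The exposure differs by outcome. Students complete the DES after the debriefing in order to rate it (9.1), and two of its subscales concern the facilitator (6.5 table), so those in one session rate the same event. The BLS checklist scores each student's own performance, where a session effect is less direct. It is not excluded: protocol section 2.1 names learning from one another's experiences as an advantage of cold debriefing.

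**Working it through.** **Inputs from the documents.** Alpha 0.05, 80% power, 26 per group and 30 with allowance for withdrawal (17.1); independent t-tests (17.1 and SAP).

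**Inputs assumed.** Session size m, ICC 0.01 to 0.10, and a standardised difference d = 0.8 for power. The documents give none of these.

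**The plan's own figures.** With ICC = 0, simulation of the planned t-test gives a type I error of 4.8 to 5.2%, so the stated 5% holds under independence. A two-sided two-sample t-test with d = 0.8 needs 26 per group (power 80.7%), which matches the stated number, but d = 0.8 is not the protocol's input. Its eta squared of 0.25 gives f = √(0.25/0.75) = 0.577, d = 2f = 1.155 and 13 per group. That mismatch is a separate matter; d = 0.8 is used below only as an assumption.

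**Type I error with clustering.** The variance of an arm mean is multiplied by the design effect DE = 1 + (m − 1) × ICC. The error of the nominal 5% test is then about 2 × [1 − Φ(1.96/√DE)]. For m = 3 and ICC 0.10, DE = 1.20, 1.96/√1.20 = 1.789, and the error is 7.4%.

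| Students per session | ICC | DE | Formula | Simulated (30 per arm, 40,000 trials) |
|---|---|---|---|---|
| 3 | 0.01 | 1.02 | 5.2% | 5.2% |
| 3 | 0.05 | 1.10 | 6.2% | 6.1% |
| 3 | 0.10 | 1.20 | 7.4% | 7.4% |
| 5 | 0.01 | 1.04 | 5.5% | 5.4% |
| 5 | 0.05 | 1.20 | 7.4% | 7.6% |
| 5 | 0.10 | 1.40 | 9.8% | 10.0% |
| 10 | 0.01 | 1.09 | 6.0% | 6.2% |
| 10 | 0.05 | 1.45 | 10.4% | 10.3% |
| 10 | 0.10 | 1.90 | 15.5% | 15.8% |

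**Which rows are likely.** Assume students are scored one at a time for up to 5 minutes each. Three students take 3 × 5 = 15 minutes with one assessor, or two rounds = 10 minutes with two. Ten students take 50 or 25 minutes. In the hot arm this queue would delay a debriefing meant to be immediate; in both arms it would delay a post-test meant to be immediate. Ten minutes for a five-domain debriefing also points to small groups. None of this fixes the size.

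**Does a session-level test repair the error?** A t-test on session means has a simulated error of 4.8 to 5.2% with at least two sessions per arm. If the arms differ in number of sessions, the Welch form stays at about 4.7 to 5.5%, whereas the pooled form can fall to between 1.2 and 4.3%.

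**Power of the session-means test.** With k = 30/m sessions per arm, df = 2k − 2 and noncentrality d × √(30/(2 × DE)). For m = 3 and ICC 0.10 this is 0.8 × √(30/2.4) = 2.83 on 18 df, giving 76%.

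| ICC | 3 per session | 6 per session | 10 per session |
|---|---|---|---|
| 0.01 | 83% | 76% | 61% |
| 0.10 | 76% | 60% | 41% |

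The ordinary t-test under independence has 86% power with 30 per arm and d = 0.8.

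**The case against.** The strongest reply is that the size of the problem is wholly assumed. Session size, number of sessions and ICC are unknown; at ICC 0.01 with three students per session the error is 5.2%, which nobody would act on. The study outcome named in section 6.1, BLS competence, is scored student by student. One person may lead every session, as section 6.1 may suggest for the cold arm ("The researcher will do a cold debriefing (after one-day post-simulation) for undergraduate nursing students in the intervention group"), and that would reduce variation between sessions. All of this stands, and it is why the point is conditional. It does not remove the point: a single facilitator leaves shared discussion in place, and individual randomisation balances students beforehand but does not make their scores independent after group delivery.

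Three stronger readings are tempting, and the documents do not support them.

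- A reader might infer that sessions cannot be identified at all. The documents show only that no identifier is listed. Section 6.5 is not exhaustive, since completion status (6.1), contact details and interest in phase 2 (6.6) are also recorded, and REDCap keeps audit trails. Sessions may be recoverable, though nothing in the plan asks for it.
- A reader might infer that cold sessions could be large because they need not follow the first simulation at once. The immediate post-test limits the cold arm in the same way as the hot arm.
- A reader might infer that both planned tests must be replaced. With session size and ICC unknown, and a loss of power even at ICC 0.01, that goes further than the evidence allows.

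**Conclusion.** The omission is clear: delivery is in groups, the tests for hypotheses 1b and 2 ignore it, and no session identifier is listed. Its effect is conditional on a positive within-session correlation. Under the assumptions of 30 per arm and ICC 0.01 to 0.10, the true level of the nominal 5% test is about 5.2 to 7.4% at three per session, 5.4 to 10.0% at five and 6.2 to 15.8% at ten, with the lower figures more likely. The DES comparison is the more exposed of the two.

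A reader might conclude that the reported p-values are wrong. The documents do not show that. They show that nobody can tell whether the excess is negligible or material until session sizes and membership are known. The point should be addressed, but it does not by itself invalidate the planned analysis.

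**What to change.** 1. Record a debriefing-session identifier in REDCap. If sessions have already run (the SAP is written in the past tense), rebuild it from the schedule.
2. Report session sizes and the number of sessions in each arm.
3. Beside the planned t-tests, report a t-test on session means, chiefly for the DES and also for BLS. Use the Welch form if the arms differ in number of sessions. No rule for switching tests by number of sessions is needed. Where the two analyses disagree, interpret p<0.05 with caution.
4. A random intercept for session is an option, but with few sessions its error rate depends on the software. With 5 to 6 sessions per arm and ICC up to 0.10, simulation gives about 1.9 to 3.9% if the degrees of freedom stay at 2k − 2 when the session variance is estimated as zero, and about 3.3 to 4.7% if the zero component is dropped. State which convention applies.
5. If an arm had only one session, report as a limitation that session and arm are confounded; no analysis can separate them.

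The cost is one data field, one extra analysis, and wider intervals and lower power in that analysis, by the amounts shown in the power table. The planned tests remain in the report.

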| | There are a total of 183 senior undergraduate nursing students and 204 third year undergraduate nursing students. Based on G*Power 3.1, the recommended sample size will be 26 participants in each group. Still, because there is a possibility that participants may withdraw from the study, the total number will be 30 participants in each group. |
| | 
3.2 Describe the time that you will devote to conducting and completing the research, i.e. percent effort.
 |
| | The PI will devote 100 percent of his time to this study. |
| | 
3.3 Describe the availability of medical or psychological resources that subjects might need as a result of an anticipated consequences of the human research.
 |

TEMPLATE: RESEARCH PROTOCOL

| NUMBER | ACTIVE DATE | PAGE |
|---------|-------------|---------|
| HRP-503 | 02-04-2020 | 7 of 40 |

at any time, they can. In case of persistent stress or discomfort, the students' wellbeing center is ready to help them.

3.4 Describe your process to ensure that all persons assisting with the research are adequately informed about the protocol, the research procedures, and their duties and functions.

All members of the study team will be required to complete the web-based University of Cincinnati Collaborative Institutional Training Initiative (CITI) program. Additionally, the study team will be informed about the study protocol, the research procedures, and personnel's respective duties and functions. The study team will meet at least once bi-weekly to discuss the study progress. The study team will sign a conflict-of-interest form and provide their current CITI certification

3.5 Describe the facilities you have access to that will allow you to conduct the research.

The setting of the study will be held in the simulation Lab at the University of Cincinnati (UC) College of Nursing (CON). The CON has a large skills lab comprised of three rooms located on the 1st floor and a simulation collaboratory located on the 3rd floor.

The PI has a private office at the CON with telephones for subject enrollment and laptop computers using Microsoft Office Software and JMP statistical software. The laptops are connected to the UC Academic Health Center Server and is internet accessible. The PI has access to a secure computer research server for data storage. There is convenient access to facsimile transmission, e-mail, and photocopying equipment. Administrative assistance is also available.

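### Cold-arm students wait 24 hours before their debrief, and nothing in the protocol or SAP discourages or records sharing of debrief content by students already debriefed on the same scenario

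*Protocol*

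**What the plan says.** Protocol section 6.2 sets the timing. For the control arm, "participants in the hot debrief group will do their post-test immediately after their debrief on the same day as the simulation". For the intervention arm, "the cold debrief participants will do the simulation, wait 24 hours, have the debrief, and will do an immediate post-test". Both arms return 24 hours after the first post-test for a second one. Section 6.2 adds: "The same simulation and BLS Assessment checklist will be conducted at baseline, post-test, and second post-test". It also says that "students will do a group debriefing".

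Allocation is by individual. Section 6.1 states: "The researcher will assign the participants to a control or experimental based on number generator". Section 3.1 gives the source population: "There are a total of 183 senior undergraduate nursing students and 204 third year undergraduate nursing students". Section 3.5 places the study in the simulation lab of one college, and section 9.2 gives the enrolment window as "From 08/24/23 to 11/01/23".

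Section 17.1 tests hypothesis 1b (greater competence with cold debriefing) by an independent t-test between arms. The SAP repeats that test. Neither mentions contact between participants.

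**The concern.** Debrief timing is the only thing that differs by design between the arms. Section 2.1 argues for the delay partly because it lets learners reflect on their own performance. Hearing the debrief from someone who has already had it is a different exposure from reflecting unaided.

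The opportunity is one-sided. Only cold students have an undebriefed interval of a day before their first post-test, and the debriefed participants come from the same two year groups. If content passes during that day, the cold arm no longer cleanly represents delayed debriefing. As planned, the trial collects nothing that would show whether this happened, so the question would stay open whichever way hypothesis 1b came out.

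**Working it through.** **1. The two schedules side by side (sections 6.2 and 13.1)**

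| | Day 1 | Day 2 | Day 3 |
|---|---|---|---|
| Hot | Simulation, debrief, first post-test | Second post-test | – |
| Cold | Simulation | Debrief, first post-test | Second post-test |

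Section 17.1 does not name the post-test used for hypothesis 1b. The cold arm's undebriefed day precedes both.

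**2. Can hot and cold students overlap?** Section 6.1 randomises after the pre-test, and section 6.2 describes assignment before it. Under either order, nothing schedules the arms apart. Accrual is 60 of 183 + 204 = 387 students (60/387 = 15.5%) over about ten weeks. Overlap is possible, but no timetable shows how common it would be.

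**3. Is there a safeguard?** The procedures (6.2), risk text (6.3, 15.5), data security (17.2) and privacy text (19.1) protect participants and their data. None concerns passing on scenario or debrief content. The analysis text (17.1 and the SAP) plans no check.

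**4. Direction.** Let δ be the true cold-minus-hot difference in SD units and c the fraction of cold students exposed.
- If exposed students score as hot students do, the expected difference is (1 − c)δ, which is smaller than δ.
- If exposure instead adds b SD to their scores, it is δ + cb, which favours cold.

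**5. Illustration only.** The documents give no contamination rate and no SD. The nearest stated figure is 26 per group. The inputs in section 17.1 do not reproduce it: a repeated-measures ANOVA at eta squared 0.25 (f = √(0.25/0.75) = 0.577), with 2 or 3 time points and an assumed correlation of 0 or 0.5, needs 4 to 10 per group. A two-sided t-test at an assumed d = 0.8 does give 26. Power is the probability that a noncentral t with 2n − 2 df and noncentrality d√(n/2) exceeds the two-sided 5% limits. At n = 26 the noncentrality is 0.8 × √13 = 2.88 and power is 80.7%.

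The dilution columns take d = 0.8(1 − c). The last column takes no timing effect and a shift of cb, with b from 0.5 to 0.8.

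| c | d after dilution | Power, 26 per group | Power, 30 per group | False rejection, 26 per group |
|---|---|---|---|---|
| 0% | 0.80 | 80.7% | 86.1% | 5% |
| 10% | 0.72 | 72.1% | 78.3% | 5.4–5.9% |
| 20% | 0.64 | 61.9% | 68.4% | 6.4–8.7% |
| 30% | 0.56 | 50.8% | 56.9% | 8.3–13.6% |

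In the dilution columns c is the fraction of the contrast lost. The values of c, b and d are all assumptions. The table shows that both directions are possible, and it estimates neither.

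**The case against.** The strongest reply is that little of value can leak. Cold students have already performed the scenario before the wait, so a classmate cannot reveal it to them. Correct BLS technique is published, and certification is recorded at baseline. Corrections to someone else's performance are not one's own debrief, and both arms receive the full debrief before their first post-test. All of this stands. It limits the likely effect but does not remove it, because the debriefed scenario is the one scored again.

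Four stronger readings are tempting, and the documents do not support them.
- A reader might infer that cold students in fact wait among debriefed classmates. Without a timetable, that is inference.
- A reader might infer that hot students are debriefed on the checklist. Section 6.5 assigns the PEARLS tool to the debrief; the checklist is the assessment instrument.
- A reader might infer that students tested earlier, by telling later ones what is scored, bias hypothesis 1b. That would affect baseline in both arms and is balanced in expectation by randomisation. Baseline scores also allow drift over enrolment to be examined.
- A reader might infer that the trial's only between-arm contrast is at risk. Hypothesis 2 also compares the arms.

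Finally, the information sheet is not among the documents reviewed. The absence of a safeguard is established for the protocol and SAP only.

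**Conclusion.** The concern holds as a possibility that the design leaves open. Cold students may hear debrief content during the 24-hour wait, and the protocol and SAP neither discourage nor record it. This could shrink a true timing effect or favour cold in hypothesis 1b. A reader might take the illustrated power loss as the expected consequence, but it rests on an assumed d of 0.8 and on dilution alone. Size and direction cannot be determined from the documents. The conclusion itself needs no numerical assumption, only that hot and cold participants can meet during the wait, which individual randomisation within one college permits. This is a cheap improvement, not a flaw that invalidates the comparison.

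**What to change.** - **Section 6.2 and the information sheet:** ask every participant at baseline not to share scenario or debrief content with other students outside study sessions until enrolment and testing end. State that group debriefings and Phase 2 focus groups are exempt; otherwise the request would bar the intervention and the qualitative phase.
- **REDCap, before each post-test:** add one yes/no item asking only whether the student has discussed the scenario or debrief with another student outside study sessions. Keep it separate from self-review or practice, since reflection during the gap is part of the rationale for cold debriefing.
- **Section 17.1:** report the answers by arm descriptively. Keep all randomised students in the hypothesis 1b analysis, and do not exclude those who answer yes. Cold students have a full day in which to answer yes before the first post-test and hot students only a short same-day interval, so exclusion would fall mainly on one arm after randomisation.

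The cost is one instruction, one REDCap item and one descriptive table. Sample size, visits and main tests are unchanged. The answers are self-reported and compliance cannot be enforced, so the change reduces and documents sharing but does not rule it out.
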